(Primary Objective 1) To establish proven currently utilized methodologies for sample collection and concomitant DNA extraction for metagenomic sequencing from the HMP JumpStart ([name] and [name]) and UH2 Demonstration Projects ([name]) with already scheduled NCS visits and self-sampling. *Sample the vaginal microbiome at the scheduled third trimester NCS clinical visit *Sample the placental and fetal (first meconium) microbiomes at the time of delivery *Self-sample stool microbiomes at scheduled intervals of one month and 6 months

(Primary Objective 2) To develop and refine protocols to enable banking of acquired specimens prior to microbial DNA extraction in an effort to establish feasibility of deferring metagenomic sequencing and analysis of some of the samples collected through NCS, and to enhance ease of collection of high quality specimens in the context of a large multicenter study that can be used for both DNA and RNA extraction and metagenomic/metatranscriptomic analysis.

With our formative approach executed as a one year demonstration project executed jointly by investigators at the Waukesha County Vanguard Center (WCVC) and at Baylor College of Medicine (BCM) employing samples collected in conjuncture with a modified Vanguard protocol, we will demonstrate not only feasibility with easily expanded NCS protocols and HMP metagenomics infrastructure, but the ability to yield unparalleled insight into functional variation of the microbiome across diverse racial and socioeconomic populations with developmental exposures. Of note, it is important to comment that our proposed protocol reflects the ultimate intent by the investigators on this LOI with respect to what will define a “full scale” NCS initiative on microbiome research.

Section E: Protocol Risks/Subjects

E1. Risk Category

(45 CFR 46.404) Category 1: Research not involving greater than minimum risk.

E2. Subjects

Gender:
Both

Age:
Adolescent (13-17 yrs), Adult (18-64 yrs), Infant/Toddler (0-36 mos), Premature Infant (<37 weeks gestational age)

Ethnicity:
All Ethnicities

Primary Language:
English

Groups to be recruited will include:
Both patients and healthy, non-patient, normals

Vulnerable populations to be recruited as subjects:
Children, Emancipated minors, Pregnant women

Vulnerable populations require special protections. How will you obtain informed consent, protect subject confidentiality, and prevent undue coercion?

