Informed consent will be obtained according to federal regulations and BCM and its affiliated hospital policies. Pregnant women will be informed of the objectives of this study by their obstetrician, primary nurse or study personnel at the time of the office visit during the third trimester of pregnancy.

The procedures involved will be described and the subjects will be asked if they would like to participate. The subjects will be made aware that there is no compensation for participation, and their care will not be altered as a result of their participation. No access to care will be withheld if subjects decline participation. Full disclosure of the nature of participating in the study will be made. The consent form will include a statement regarding long term storage of the samples. Subjects will be made aware their participation involves the analysis of genetic material, including the potential for genome wide association studies wherein the results of their DNA code will become part of public archives.

Subjects will further be made aware that confidentiality will be protected within the limits allowed by law. This will include using unique study identifier codes such that samples and data (including genetic data) cannot be linked to a subject or their child.

E3. Pregnant woman/fetus
Will pregnant women be enrolled in the research?

Yes

E4. Neonates

Will neonates be enrolled in the research?

Yes

E5. Children

Will children be enrolled in the research?

Yes

Section F: Design/Procedure

F1. Design

Select one category that most adequately describes your research:

c) Pilot

Discuss the research design including but not limited to such issues as: probability of group assignment, potential for subject to be randomized to placebo group, use of control subjects, etc.

This study is designed to collect a total of three sets of samples from women and their offspring in a feasibility study for formative research with the National Children's Study. Of note, all investigator obtained sample collection points correspond with existing visits within the currently approved NCS protocol ([name], PI).

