Will you obtain a Certificate of Confidentiality for this study?

No

Please further discuss any potential confidentiality issues related to this study.

Section L: Cost/Payment

Delineate clinical procedures from research procedures. Will subject's insurance (or subject) be responsible for research related costs? If so state for which items subject's insurance (or subject) will be responsible (surgery, device, drugs, etc). If appropriate, discuss the availability of financial counseling.

Patients will not be charged to participate and all ensuant costs to the research will be covered by the study grant.

If subjects will be paid (money, gift certificates, coupons, etc.) to participate in this research project, please note the total dollar amount (or dollar value amount) and distribution plan (one payment, pro-rated payment, paid upon completion, etc) of the payment.

Dollar Amount:

100

Distribution Plan:

Single payment following receipt of final specimen. In instances of fetal or neonatal or infant demise, remuneration will occur with last specimen received.

The rationale for deferring payment until the final specimen is received, rather than by study visit, is that the design of the study requires complete data sets.

Section M: Genetics

How would you classify your genetic study?

Discuss the potential for psychological, social, and/or physical harm subsequent to participation in this research. Please discuss, considering the following areas: risks to privacy, confidentiality, insurability, employability, immigration status, paternity status, educational opportunities, or social stigma.

Not applicable, as this a microbiome metagenomics study and host DNA is not analyzed.

Will subjects be offered any type of genetic education or counseling, and if so, who will provide the education or counseling and under what conditions will it be provided? If there is the possibility that a family's pedigree will be presented or published, please describe how you will protect family member's confidentiality?

Not applicable.

Section N: Sample Collection

SAMPLE: Other: Vagina

What is the purpose of the sample collection?

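### Section E2 tells women there is no compensation, Section L pays them $100, and the payment rule leaves its trigger and early stopping undefined

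*Protocol*

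**What the plan says.** Section E2 of the protocol answers an ethics-board question about vulnerable subjects: "How will you obtain informed consent, protect subject confidentiality, and prevent undue coercion". As part of the answer it says: "The subjects will be made aware that there is no compensation for participation".

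Section L gives a dollar amount of 100. Payment is made once, with one exception: "Single payment following receipt of final specimen. In instances of fetal or neonatal or infant demise, remuneration will occur with last specimen received". The reason given for deferring payment, "rather than by study visit, is that the design of the study requires complete data sets".

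Under Section F1 each woman provides a vaginal sample at 28 weeks, placental and meconium samples at delivery, and infant stool at one and six months, collected at home and sent in. Primary Objective 1 in Section D includes this home stool collection.

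**The concern.** Two current statements in one protocol tell staff opposite things about payment. The Section E2 statement is part of the answer on how pregnant women, emancipated minors and children are protected from coercion. If Section L is what happens, that part of the safeguard is untrue.

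There is also a measurement issue. The study asks whether microbiome sampling can be added to a large cohort, and return of home stool kits is part of that question. A return rate can be interpreted only if the reader knows what women were offered for the kit. With one section saying nothing and another saying $100, the protocol does not fix that condition.

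Finally, the payment rule is incomplete. It depends on an undefined event and covers only one of the ways in which a woman might not reach it.

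**Working it through.** No plan figure needs reproducing. The check compares the sections and adds a little arithmetic.

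**1. Can Sections E2 and L be reconciled?**
- *Is E2 about cost to the woman?* No. Section L says separately that patients will not be charged, and E2 speaks of compensation for taking part.
- *Do the two statements apply to different sites?* No. Both stand in the local (BCM) protocol. Section F1 says the second site works under its own.
- *Is one superseded?* Nothing in the text marks either as replaced.

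The contradiction stands.

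**2. The Section L rule, case by case**
- *All specimens supplied:* $100.
- *Six-month stool sent, an earlier specimen missed:* $100 if final means the last one scheduled; nothing if it means the last of a complete set. The text does not settle this.
- *Withdrawal or loss before the six-month stool, no demise:* no payment is provided for. Section N does foresee withdrawal, where it deals with destruction of samples.
- *Fetal, neonatal or infant demise:* paid with the last specimen received, although the set is incomplete.

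**3. Does the analysis explain the stated reason?** Section L says that "the design of the study requires complete data sets". Section G2 compares fresh extraction with banking on parallel samples from each subject, using a random 20% of banked specimens (10% for each of two banking protocols). The comparisons listed are read length and quality, taxonomic interpretation, and variation by clinical factors. A pair of parallel samples from one collection can enter the fresh-versus-banked comparison whether or not the same woman supplied the other collections.

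**4. Scale**
- Wait from first sample to payment, assuming birth at 40 weeks and taking six months as 26 weeks: (40 − 28) + 26 = 38 weeks.
- Maximum outlay at the local site: 30 × $100 = $3,000.
- Illustration only: if 10% to 20% of the 30 women missed the last kit (an assumption; the protocol gives no rate), 0.10 × 30 = 3 to 0.20 × 30 = 6 women would be unpaid after giving up to four of five specimens.
- If the same $100 were pro-rated: $100 / 5 specimens = $20 each, or $100 / 4 collection times = $25 each. The amount tied to the six-month kit would fall from $100 to $20 or $25.

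**The case against.** **The consent forms govern what women read.** Section Q lists two forms, and their text is not available here. A reader might infer that women were in fact misinformed in writing. The documents do not show that; the forms may state the payment correctly. What stands is that the protocol's own description of the consent discussion conflicts with its payment section.

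**The rule does reward complete sets.** A reader might infer that payment bears no relation to completeness, because a woman could skip the one-month stool and still be paid. That depends on one reading of an undefined term. Withholding the money until the end rewards staying to the end, and the demise exception is a stated humane provision. Only the lack of definition stands.

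**Retention.** A reader might also infer that the payment scheme distorts retention. The protocol gives no dropout or return figure, and paying at the end would, if anything, favour return of the last kit. Reminder calls (Section J2) and support from cohort staff also work towards retention. This objection stands in full.

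**Complete sets may be wanted for another reason.** Primary Objective 1 spans the third trimester, delivery, one month and six months, so showing that a full series can be collected is a plausible aim. That is fair. But Section L appeals to the design without saying so, and the comparison in Section G2 does not supply the reason.

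**A single payment on completion is a legitimate choice.** The form offers it alongside pro-rating. Pro-rating has a cost of its own: less money attaches to the six-month kit. If paid per specimen, it could also cost a woman money when paged staff miss a delivery sample. This stands, so pro-rating is an option rather than a requirement.

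**Conclusion.** The concern holds as a contradiction with an incomplete rule attached. Sections E2 and L cannot both be true, and E2 is the one that would mislead women at consent. This rests on the text alone and needs no assumption. It concerns the 30 local subjects; the second site's payment terms are not shown.

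That Section L leaves the final specimen undefined, and provides nothing for early stopping without a demise, is equally plain from the text. The mismatch between the stated reason and the analysis is weaker: the reason is unexplained, not shown to be wrong.

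No effect on retention can be sized. The 3 to 6 women above illustrate an assumed 10% to 20% and are not an estimate. In a minimal-risk pilot this should be corrected, chiefly because it affects what women are told and the condition under which kit return is observed.

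**What to change.** 1. In Section E2, replace the statement on compensation with the $100 payment and the condition for receiving it.
2. Check that both consent forms listed in Section Q say the same.
3. In Section L, define the final specimen, and state what is paid on withdrawal and when an intermediate specimen is missed.
4. Either explain which objective needs complete sets or drop that reason.
5. Report the stool return rate as obtained under the stated payment.

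Pro-rating the same $100 across collection times is one way to settle item 3. It keeps the $3,000 local ceiling and pays women who stop early for what they gave, but leaves a smaller incentive for the six-month kit. Keeping a single payment is also workable if the rule is fully stated and disclosed.

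The cost is wording in two sections, a check of two consent forms and, if pro-rating is chosen, small partial payments to women who stop early. Sampling, sample size and analysis do not change.

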Finally, the impact of both host phenotype and the environment on microbial community establishment, notably in childhood, is poorly understood. One notable exception is the impact of obesity on the gut microbiome. In twin studies of adult female monozygotic and dizygotic twin pairs concordant for leanness or obesity and their mothers, it has been demonstrated that obesity is associated with phylum-level changes in the microbiota and reduced bacterial diversity. Broad environmental and exposure measures, such as those acquired in the full scale NCS study, will further allow us to understand broad phenotypic and environmental influences on concomitantly derived microbial profiles in humans. For the purposes of this NCS demonstration project, “exposure” will be defined by known proximal influences including mode of delivery, breast milk versus use of formula, and other limited measures (i.e., antibiotic exposure, gestational age, and length of hospital stay). In addition, these known influences on microbial diversity serve as our rationale for the number of subjects necessary to determine feasibility.

Section D: Purpose and Objectives

In this NCS Formative Research Study our broad objective is to lay the essential groundwork establishing the feasibility of a full-scale microbiome research effort in the National Children's Study.

By way of overview, construction of a reference sequence data set for the Human Microbiome Project (HMP) was undertaken in 2007 as an NIH Road Map Initiative with the aim to fully characterize the microbiome, and is an ongoing effort at multiple centers notably including Baylor College of Medicine (JumpStart initiative, [name] and [name] co-Investigators). In our current expanded proposal with the NCS, we collectively propose to: (1) jointly leverage our microbiome genomic sciences infrastructure developed for HMP with the clinical and longitudinal data and sample collection infrastructure of the NCS, then (2) refine, optimize and ultimately establish protocols to bank NCS-acquired microbial specimens for future metagenomics analyses on the human microbiome. When applied to the full scale NCS study, our collaborative formative approach will enable a comprehensive interrogation of the human gut microbiome from establishment, to birth, and into early adulthood. Successful accomplishments of the following goals will enable achievement of our overall study aims:

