RNA extraction: In order to assess potential feasibility of employing concomitant transcriptomics analysis in banked specimens, RNeasy or NucleospinII will be employed to extract RNA from the "banked approach" specimens. Given the timeline and expense associated with transcriptomics, demonstrative analysis will be deferred. Alternately, RNA yield and integrity will be assessed by standard Sybr and Nanodrop methodologies.

Metagenomic sequencing and analysis: All samples, whether collected and extracted at the BCM site or the WCVC site, will be shipped to BCM for metagenomic sequencing and analysis.

Sequencing overview: The predominant metagenomics sequencing strategy will focus on 16S rDNA 454 sequencing. This takes advantage of existing and fully functional technology and pipelines with proven reproducibility and quality reads in a self-sampled pediatric population. In addition to bacteria, archaea are surveyed by the addition of different primer sets to amplify archaeal 16S rDNA sequences, and fungi are identified by 18S rRNA gene/ITS-based sequencing. Sequencing of the bacterial 16S rRNA gene targets will be performed in collaboration with the existing HMP Genome Sequencing Centers (Baylor College of Medicine, Washington University Genomics Center, and the Broad Institute) by 454 GS Titanium sequencing. A detailed presentation of metagenomics DNA sequencing, informatics/biostatistics, and DNA sequencing approaches, is outside the scope of this protocol, but suffice it to say we are employing our present and proven methodology for sequencing, informatics pipelining, and analysis. All data are maintained on secure servers, in a coded (deidentified) fashion.

Bioinformatics overview: Read data will be filtered and analyzed so that accurate taxonomic assignments may be made while the HMP is completing its initial JumpStart phase, next-generation sequencing and analysis

approaches have been optimized, including our first analysis of 18 pregnant reference subjects (H-25849), and therefore further methodologic details are not included in this protocol.

Section G: Sample Size/Data Analysis

G1. Sample Size

How many subjects (or specimens, or charts) will be used in this study?

Local: 30 Worldwide: 120

Please indicate why you chose the sample size proposed:

This formative study seeks to evaluate feasibility of incorporating routine microbiome sampling as part of the National Children's Study (NCS).

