The majority of sample collection (90 of 120 subjects) will take place at WVCV, where participant enrollment began in 2008 and averages 10 to 12 NCS births per month with anticipated increasing accrual. A smaller cohort of participants (30 of 120 subjects) will be enrolled at BCM.

BCM, although not currently enrolling in the Vanguard pilot, has established and optimized approaches for microbial sampling of vagina, placenta, meconium, and feces, through participation in the HMP JumpStart and HMP Clinical Demonstration Project (UH2) initiatives and will thus serve as a measured control against any methodological concerns related to microbial sampling and nucleic acid extraction (see prior referenced IRB approved protocols).

The combined involvement of these sites will leverage the NCS experience and extensive environmental data collection of WVCV with the HMP metagenomics infrastructure at BCM, and allow us to evaluate the feasibility of adding microbiome sampling and metagenomic analysis to the NCS.

G2. Data Analysis

Provide a description of your plan for data analysis. State the types of comparisons you plan (e.g. comparison of means, comparison of proportions, regressions, analysis of variance). Which is the PRIMARY comparison/analysis? How will the analyses proposed relate to the primary purposes of your study?

Outline of goals and strategies for the collection, analysis, and characterization of metagenomics data from NCS acquired specimens employing established methodology from the HMP JumpStart initiative have been previously outlined.

Briefly, our collaborative proposal will use a two layered analysis strategy.

We will collect microbial specimens (n=120 gravidae, 90 from WVCV and 30 from BCM) at NCS specified timepoints, and aliquot specimens for both fresh extraction and banked specimen protocols. We will extract nucleic acids from at the time of specimen collection and subsequently subject such immediate extractions to flash freezing for later batched-run metagenomic sequencing and analysis. In the second-layer strategy, we will collect parallel samples from each subject for immediate banking (using 1 of 2 "banking" protocols) rather than already proven immediate nucleic acid extraction. A randomly-selected cohort comprising 20% (10% of each of

the two banking protocols) of these “banked” specimens will be run in batched parallel samples in order to establish and refine banking methodology.

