We will thereafter compare the methodologic approaches with respect to: 1. Length and quality of sequencing reads 2. Interpretation of reads by virtue of taxonomy (phyla, taxa, genus, species) and OTU binning 3. Variation in read quality, length and interpretation by virtue of known clinical factors (mode of delivery, BMI, method of feeding as breast or bottle with formula).

In such a manner we will dually assess and demonstrate not only feasibility and methodology as outlined above, but establish banking protocols for the full scale NCS.

Section H: Potential Risks/Discomforts

H1. Potential Risks/Discomforts

Describe and assess any potential risks/discomforts and assess the likelihood and seriousness of such risks:

The potential risks/discomforts are minimal. Slight irritation at the sampling site (vagina) may occur and some subjects may experience embarrassment at having the procedure. The placental, meconium and fecal sampling pose no additional risks to the subjects since no invasive procedures are used to collect this material.

H2. Data and safety monitoring plan

Do the study activities impart greater than minimal risk to subjects?

No

H3. Coordination of information among sites for multi-site research

Is the BCM Principal Investigator acting as the SPONSOR-INVESTIGATOR for this multi-site research?

Yes

Is BCM the COORDINATING CENTER for this multi-site research?

Yes

If the answer to EITHER of the questions above is "Yes", please complete the following questions:

If this is a multicenter study and the BCM PI is an INVESTIGATOR with responsibilities of SPONSOR or if BCM is the COORDINATING CENTER, describe the management of information among the sites related to participant protections. Your description should include reporting of unanticipated problems, protocol modifications, IRB and/or institutional approvals, and interim results among the sites.

The laboratories of Drs. [name], [name], and [name] at Baylor College of Medicine will process all samples obtained from this formative project on the human microbiome within the NCS. Metagenomic sequencing will be run in the Human Genome Sequencing Center and data will be downloaded onto secure

servers in a manner consistent with aforementioned protocols presently employed for the Human Microbiome Project.

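### Feasibility of sampling is the stated question, but the comparisons said to show it all start from a sequenced specimen, so failed collections enter no planned result

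*Protocol*

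**What the plan says.** **The question.** Section G1 opens its sample size answer with "This formative study seeks to evaluate feasibility of incorporating routine microbiome sampling" in the National Children's Study (NCS). Primary Objective 1 in Section D covers a vaginal sample at the third-trimester visit, placenta and first meconium at delivery, and home-collected infant stool at one and six months. Primary Objective 2 concerns banking of specimens before extraction.

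**The analysis.** The form for Section G2 asks which comparison is primary and how the analyses relate to the study's purposes. The answer describes fresh extraction alongside banked aliquots and continues: "We will thereafter compare the methodologic approaches with respect to: 1. Length and quality of sequencing reads". The second item is interpretation of reads by taxonomy and OTU binning. The third is variation in read quality, length and interpretation by mode of delivery, BMI and feeding. The closing sentence says that feasibility and methodology are assessed and demonstrated in this way.

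**The sample size.** G1 gives "Local: 30 Worldwide: 120" and "The majority of sample collection (90 of 120 subjects) will take place at WVCV", with the other 30 at Baylor College of Medicine (BCM). The background text before Section D says that known influences on microbial diversity "serve as our rationale for the number of subjects necessary to determine feasibility", but G1 derives no number from them.

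**Payment.** Section E2 says subjects will be told "there is no compensation for participation". Section L sets a single payment of 100 dollars after the final specimen. It explains that the reason for not paying by visit "is that the design of the study requires complete data sets".

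**The concern.** A study of whether sampling can be added to routine visits has to count the occasions on which sampling did not work. The three G2 comparisons begin only once a specimen has been collected, has reached the laboratory, and has been extracted and sequenced. Losses before that point change how many specimens are compared, but no planned result reports them.

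The protocol itself treats these early steps as needing effort. Section J2 provides a pager for study staff at delivery, weekly calls from 32 weeks, and reminder calls for home sampling. Section F2 relies on families freezing gel packs and packing a cold box. These steps would decide whether a full-scale NCS could collect the material, yet their success rate is not an outcome. With no rate, no denominator of enrolled women and no criterion, a high or a low capture rate could equally be followed by a statement that sampling is feasible.

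The payment conflict also bears on this. A sum paid only after the last specimen may raise completion, so whether women expect it affects the rate that a feasibility study should report.

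**Working it through.** **1. The plan's own figure.** 90 + 30 = 120, so the total reproduces as a sum. Nothing further can be reproduced, because the protocol gives no expected collection rate, precision target, power, alpha or feasibility threshold.

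**2. What each planned assessment can see.** Section F1 implies five specimens per mother-infant pair: one vaginal, one placental, one meconium and two stools. Over 120 women that is 5 x 120 = 600 expected specimens.

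| Planned assessment | Needs | Counts a specimen never collected or returned? | Counts a failed DNA extraction? |
|---|---|---|---|
| Read length and quality (G2) | reads | no | no |
| Taxonomy and OTU binning (G2) | reads | no | no |
| Variation of these by clinical factors (G2) | reads | no | no |
| RNA yield and integrity (F2) | a banked specimen in hand | no | no |

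The RNA check does not use reads, but it starts from specimens already collected and has no denominator of enrolled women.

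**3. What the design could estimate.** Take all enrolled women as denominator n, with x of them having the specimen in question. The exact (Clopper-Pearson) 95% interval is

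- lower limit = the 0.025 quantile of Beta(x, n - x + 1)
- upper limit = the 0.975 quantile of Beta(x + 1, n - x)

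The rates below are assumptions, because the protocol states none.

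| Assumed observed rate | n = 120 (both sites) | n = 90 (Waukesha) | n = 30 (BCM) |
|---|---|---|---|
| 80% | 96/120: 71.7-86.7% | 72/90: 70.2-87.7% | 24/30: 61.4-92.3% |
| 90% | 108/120: 83.2-94.7% | 81/90: 81.9-95.3% | 27/30: 73.5-97.9% |

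**4. What goes unreported now.** Suppose a stool specimen is obtained from 108 of 120 women in one case and from 72 of 120 in another. As proportions, these are 90% (83.2-94.7%) and 60% (50.7-68.8%). The intervals do not overlap, and the two results would mean different things for a full-scale study. Under G2 as written, both cases produce the same three read-based comparisons, on 108 or on 72 specimens, and neither percentage is a planned result.

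**The case against.** **This is detail for a statistical analysis plan.** Interval methods and tabulation by specimen type are commonly left to such a plan, and none is shown here. That holds for the details. It does not cover the main point, because the protocol answers the primary-analysis question itself and puts forward read-based comparisons as the way feasibility is shown.

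**The closing sentence of G2 may refer to the whole two-layer strategy, including collection, and the three comparisons mainly serve the banking objective.** This is a fair reading. It still leaves Objective 1 without an outcome, since collecting specimens from 120 women is an activity and no result is defined for it.

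**Feasibility is partly assessed elsewhere.** RNA yield and integrity are checked to judge whether transcriptomics is possible in banked material. Section G1 also gives BCM the role of a measured control for sampling and extraction concerns. So it would be too strong to say that feasibility is not assessed at all. The RNA check covers only specimens in hand, however, and the control role is attached to no stated outcome.

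**A reader might infer from Section L that only complete sets will be analysed.** The documents do not support this. The sentence explains why payment is deferred. No section excludes a woman or a specimen because a set is incomplete. Section H3 speaks of sequencing the samples of all eligible subjects, and Section L itself provides for payment when a death ends the series early. Counts of expected complete sets would therefore measure a restriction that the plan does not impose.

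**The payment terms may not reach most of the sample.** The Waukesha site works under its own IRB protocol (Section F1), so the terms for those 90 women cannot be seen here. The conflict within this protocol stands all the same.

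**Conclusion.** The concern holds for the planned outcomes. Feasibility of collection is the stated question, and none of the three G2 comparisons counts a specimen that was missed, not returned or not successfully extracted. This follows from the wording of G2 and needs no assumption about rates.

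It does not extend to a complete-case analysis, which the protocol does not prescribe, or to a claim that no aspect of feasibility is examined.

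The number of women is adequate for the missing estimate. At an assumed 80% capture rate, 120 women give an exact 95% interval of 72-87%, and the 90 at Waukesha alone give 70-88%. The 30 at BCM alone give 61-92%, which is wide. These figures depend on the assumed rate and on all enrolled women being in the denominator. The gap therefore lies in the definition of the outcome and needs no change in size.

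The contradiction between no compensation and 100 dollars is real but secondary. It is an inconsistency in what subjects are told, and it matters here only because the incentive bears on completion.

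**What to change.** 1. In G2, make this the primary analysis for Objective 1, separately for each of the five specimens: the proportion of all enrolled women whose specimen was (a) collected, (b) received in usable condition, (c) successfully extracted and (d) sequenced. Give exact 95% confidence intervals, overall and by site.
2. State a success criterion in advance. Without one, a proportion and its interval still leave any rate open to being called feasible. As an illustration only, a rule that the lower limit must exceed 80% would be met by 108 of 120 (lower limit 83.2%) and not by 96 of 120 (71.7%). The sponsor should choose the level and say how a death before a scheduled specimen is counted.
3. Keep the read-based comparisons for Objective 2, and say that they use every available specimen.
4. In G1, describe the 120 women by the precision they give for these proportions, since no other derivation is shown.
5. Reword the Section L sentence so that it cannot be taken as an analysis rule. Reconcile Section E2 with Section L on payment, and report the incentive alongside the completion rates.

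The cost is protocol wording and a specimen-tracking table. No extra subjects or assays are needed.
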